# VII. DETAILED INVESTIGATIONS IN A SUBSAMPLE OF 1000 PATIENTS (REGISTRY SUBSTUDY)

Since there is no uniform requirement of investigations other than ejection fraction or chest X-ray in the Registry, it is possible that some of the data collected from the hospital records may be biased (e.g., more tests done on the "sickest" patients). In order to obtain key data on a relatively "unselected population" that differs from the Trials substudy population and to assess the biases inherent in the main body of the Registry, 1000 stratified (see appendix D) randomly chosen patients will be studied. The following procedures are to be completed:

- M-mode and 2-D echocardiograms (to be read centrally). Doppler i) echocardiograms would be performed only at those centers participating in the SOLVD Echocardiography Substudy.
- Physical examination and history. ii)
- Drawing of blood for plasma renin and catecholamines iii) (determinations to be performed centrally).
- Seventy-minute ambulatory Holter monitoring (one hour at rest, iv) during the 6-minute walking test, and for 3 minutes post walking) (to be read centrally).
- Six-minute walking test. v)
- Chest X-ray and electrocardiogram, if not done within 90 days. vi)

Once a patient has entered the Registry, the SOLVD microcomputer data entry system will identify whether a particular patient is to be selected for the Registry Substudy. Once such a patient is identified, he/she is invited to participate in the Registry Substudy. If he/she consents and a good quality (as defined in Appendix C) echocardiogram is obtained, all the other tests are performed. If he/she refuses or a good quality echo cannot be obtained, this patient does not enter the substudy but should still be included in the main Registry. The flowchart in appendix A2 describes the procedure for the Registry Substudy clinic visit. Preferably, the visit is to be scheduled for the day the echocardiogram can be performed. If this is not possible, the echo and the rest of the procedures must be done within two weeks of each other and any major intercurrent events occurring must be documented with a Hospitalization form. The clinic visit should take place no later than 90 days after enrollment.

A brief description of each procedure follows; for details on their protocols, see Appendix C.

a) M-mode and 2-D echocardiography: The M-mode and 2-D echocardiograms will be used to provide indices of systolic and diastolic function, chamber size (LV, RV, LA and RA) and left ventricular wall thickness. Only good quality echoes (see appendix C) will be accepted. The first 5 echoes will be submitted to the SOLVD echo core laboratory for analysis and all 5 echoes should be analyzable for all key variables. Deficiencies will be immediately notified to the participating clinics. All echocardiograms will be recorded on SOLVD Registry videotape which will be transmitted to the core laboratory for central analysis. See appendix C for further details.

b) Physical examination and history. In all patients, the clinical data on the baseline form will be collected again. This will provide a comparison of the data extracted from the patient's charts versus a direct, more standardized data collection.

c) Baseline plasma renin and cathecholamine: After the insertion of an indwelling venous cannula and with the patient resting for 30 minutes in the supine position, a 20 ml sample of blood will be drawn for plasma renin and catecholamines. The blood samples will be frozen at -70 degrees centigrade and shipped in batches to the core laboratory at the University of Texas, Galveston. See appendix C for details.

d) Seventy-minute ambulatory monitoring. All patients will receive a one-hour ten-minute ambulatory monitoring while the patient is in the outpatient clinic. The period will include the 6-minute walking test. The tape will be analyzed at a central facility. Data from BHAT (Davis et al. 1986) indicate that a one-hour ambulatory monitoring may be as predictive of mortality and sudden death as 24-hour monitoring. This seems especially likely in a group of patients with a high prevalence of arrhythmias as expected in this Registry. Coupled with the convenience and low cost, a one-hour ambulatory monitoring may be a reasonable estimate of ventricular arrhythmia. See appendix C for details.

e) Six minute walking test. The distance walked in six minutes has been shown to be a reasonable assessment of the functional capacity of patients with congestive heart failure (Guyatt et al. 1985). Previous studies have shown a good correlation between the 6-minute walking test and symptoms and objective measures of functional capacity such as VO2max. See appendix C for procedures for conducting this test.

f) Chest X-ray and electrocardiogram. If not available from the preceding 90 days.

VIII. PERIOD OF PATIENT ACCESSION

The timetable for the SOLVD Registry is as follows:

	YEAR 1 December 1, 1987 - November 30, 1988
Dec. 1, 1987 - Dec. 31, 1987	Phase-in month. Major activities include training session for clinic personnel and quality control for substudy procedures.
Jan. 1, 1988 - Sept. 30, 1988	Nine-month recruitment period
Oct. 1, 1988 - Nov. 30, 1988	Two-month phase-down. Major activities include completing data col- lection of recruitment, evaluating continuation of recruitment of rare etiologies and planning for YEAR 2 follow-up activities.
	YEAR 2 December 1, 1988 - November 30, 1989
Mailing of que	estionnaire on vital statistics
	YEAR 3 December 1, 1989 - November 30, 1990
Vital status a	ascertained by the Coordinating Center with national death registries.
ч.	YEAR 5 December 1, 1991 - November 30, 1992
Vital status a	ascertained by the Coordinating Center with national death registries.
As shown in th	he timetable, patients with the more common etiologies will be enrolled

As shown in the timetable, patients with the more common ethologies will be enfolded during a 9-month period. Since only a few patients with the rarer ethologies (e.g., active myocarditis or specific cardiomyopathy) will be identified at each center per year, patients with these underlying diseases will be recruited until June 1991. A flow diagram for the SOLVD Registry is included in appendix A1.

### IX. DATA COLLECTION

Registry data will be collected in consecutive patients screened at the participating clinical centers who meet the Registry entry criteria. These will include patients who enter the randomized trials during the accession period to the Registry. The inclusion and exclusion criteria for patients entering the Registry have been previously defined. The participating centers have been described in Section III. The period of enrollment into the SOLVD Registry has been described in Section VIII.

Each clinical center will be expected to enroll at least 300 patients into the Registry, including a subset already being enrolled in the SOLVD trials. In addition, approximately 50 stratified randomly selected patients at each center will undergo additional baseline testing, including an M-mode and two-dimensional echocardiogram, a 70-minute Holter monitoring, and a 6-minute walking exercise test. These patients, aggregated over all centers to form the substudy sample, will be stratified according to the etiology of the underlying condition, to include ischemic and/or hypertensive heart disease, patients with idiopathic cardiomyopathy, and "valvular" myopathy. Attention will be specifically directed to a subset with the entry syndrome of pulmonary edema without acute MI.

### Follow-up Data

Two types of follow-up information will be obtained. First, a one-year follow-up questionnaire requesting information on vital status and hospitalizations will be administered by mail and followed, if necessary, by a telephone contact.

The one-year follow-up interview is to be attempted through the mailing of a letter that will be standard and ask the following questions on an attached form (SOLVD REGISTRY "FOLLOW-UP FORM"):

i) Have you been hospitalized during the period \_\_\_\_\_\_\_ to ? If yes, please give us the name of the hospital(s), date(s) of hospitalization(s) and the reasons for the hospitalization(s). [Note that all hospitalizations are of interest. The dates to be filled in by the clinic should reflect a one-year time period from their date of enrollment into the Registry.]

ii) Are there any other matters about your health that are concerning you? [This question will not be included in the collaborative data base.]

iii) Question number 35 of the Quality of Life form (the "ladder of life").

The body of the letter will be uniform across centers, but may contain center-specific paragraphs to continue participant rapport. The participant will be asked to complete the form with the above questions and return it. Some of the data on the form will be entered on the SOLVD REGISTRY "ONE-YEAR FOLLOW-UP INTERVIEW COVER FORM."

If contact is not established through the mail, phone calls and other means of establishing contact are to be attempted. The form can be completed over the phone.

If the participant is participating in the SOLVD trials, DO NOT attempt a mail or phone contact by the Registry. Contact information is to be obtained from the closest scheduled SOLVD trial visit occurring after one year from the SOLVD REGISTRY BASELINE FORM. Since the "ladder of life" will not be available, it must be administered at a visit close to the one year time and the code entered on the SOLVD Registry "Follow-up Form."

If the participant is acknowledged to be alive and has not required any hospitalization during the preceding year, no further information will be required at this time beyond completion of the One-Year Follow-up form. If the participant has died, the research nurse will obtain reports of hospitalizations, if any have occurred, and circumstances of death as well as the death certificate, and will forward a Designation of Death form, the Death Certificate Cover Sheet form, and Hospitalization forms (as needed) promptly to the Coordinating Center. If the participant is living but has required one or more hospitalizations during the preceding year, the nurse will obtain reports of the hospitalizations, and will complete the Hospitalization form for each hospitalization. (Copies of these forms are included in appendix B.)

It should be noted that if a participant is registered in the logbook at a participating center and subsequently dies during the same hospitalization, the center is required to seek his/her eligibility for the SOLVD Registry and to complete and submit to the Coordinating Center the Main Registry Baseline form, the Designation of Death form, and the Death Certificate Cover Sheet for this participant.

There will be a time allowance of 60 days for submitting the one-year follow-up forms to the Coordinating Center, i.e., 60 days after the anniversary of enrollment.

The second type of information derived from the follow-up of the Registry participants will be a long-term ascertainment of vital status through the National Death Index (NDI) and corresponding registries in Canada and Belgium. Although several matching criteria are available for searches of the NDI, the three absolutely essential identifiers include the social security number, the date of birth and the full name of the participant. Information on vital status will be sought approximately two years and four years after enrollment of a patient in the Registry. For the United States, this will be done at the SOLVD Coordinating Center. The Canadian centers and the Belgian center will be responsible for collecting these data from their respective Bureaus of Vital Statistics and for submitting them, upon request, to the SOLVD Coordinating Center.

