# III. PARTICIPATING CENTERS AND CAPABILITIES

All clinical centers collaborating in the SOLVD randomized trials will be invited to participate in the Registry. However, participation is not compulsory and individual centers may be free to decline. For example, if twenty centers are participating, each center will be required to enter and follow a minimum of 300 patients in the Registry. It is anticipated that at least 20% of the Registry patients at each center will also be in the SOLVD trials. Therefore, every participating center should be on target for recruitment for the SOLVD trials as a condition for participating in the Registry. In addition, each center must be willing to do high quality M-mode and 2-D echocardiograms, perform ambulatory monitoring and obtain a blood sample for renin and catecholamines in 50 patients randomly selected from their patients. Ability to do good quality echos is a condition for participation. The centers must be committed to following their patients in the Registry during the entire period of the study.

It is desirable to obtain Registry patients from one hospital site at each clinial center. Once a hospital is chosen to participate, all consecutive patients eligible for the Registry during the recruitment period of nine months must be enrolled. It is expected that around 6000 patients will be enrolled.

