10.3 State/Province:	12.2 Hospital street address:
10 4 Country:	

12.3 City:	14.2 First Name:
	15.1 Street address:
12.4 State/Province:	
12.5 Country:	
12.6 Zip Code/Canadian or European Postal Code:	15.2 City:
13. Patient hospital ID number:	
PRIVATE PHYSICIAN INFORMATION	15.3 State/Province:
14.1 Last Name:	15.4 Country:
	15.5 Zip Code/Canadian or European Postal Code:

4

SOLVD MAIN REGISTRY BASELINE FORM (screen 5 of 15) (RBF page 3 of 8)

•

16. Telephone Number (private physician):	19.1 Street address:
NEAREST RELATIVE OR FRIEND NOT RESIDING WITH PARTICIPANT	
17.1 Last name:	
	19.2 City:
17.2 First name:	
18. Relationship:	

(Nearest relative/friend continued)	D. X-RAY FINDINGS Ye	s
19.3 State/Province:	<pre>21.1 Is chest-X-ray available? Y    (If NO, skip to section E)</pre>	
19.4 Country:	21.2 Date of most recent chest X-ray (should be 7 or more days after MI, cardiac sur- gery, PTCA, or balloon valvuloplasty): ////// Month Day Year	
20. Telephone number:	21.3 Is this X-ray the qualifying X-ray? Y	
	22. Pulmonary congestion:	
	22.1 Evidence of pulmonary congestion Y (If NO, skip to Q. 23)	!
	22.2 Basal or perihilar vascular blurring	!
	22.3 Kerley B lines Y	!
	(continued)	

Т

SOLVD MAIN REGISTRY BASELINE FORM (screen 7 of 15) (RBF page 4 of 8)

	Y	es	No			Yes	No	Unreco
	Alveolar or pulmonary edema		N	24.	Indicate all of the following th rently (including etiology speci	at o fied	ccur abo	concur ve):
22.5	Pleural effusion	Y	N	24.1	Ischemic heart disease (IHD)	Y	N	U
E.	ETIOLOGY OF DISEASE	223		24.2	Hypertensive heart disease (HHD)	¥	N	U
23.1	What is the primary etiology of participa heart disease (choose only one of the fol	int's	ng):	24.3	Active myocarditis	Y	N	U
	Ischemic heart disease (IHD)		1	24.4	Idiopathic cardiomyopathy	¥	N	U
	Hypertensive heart disease (HHD)		2	24.5	Specific cardiomyopathy (ex: viral, toxic, ETOH, post-	Y	N	U
	Active syocarditis		3		partum, history of cocaine use) (If NO or UNRECORDED, skip to Q.	24.	7)	
	Valvular heart disease - aortic		4	24.6	Specify:			
	Valvular heart disease - mitral		5	24.7	Valvular heart disease - aortic	Y	N	U
	Idiopathic cardiomyopathy (specifics unknown)		6	24.8	Valvular heart disease - mitral	Y	N	U
	Specific cardiomyopathy (ex: viral, toxic, ETOH, postpartum, history of cocaine use) (If none, skip to Q. 24)		7					
23.2	Specify:		-		•			

-----

F. RELATIONSHIP TO SOLVD TRIALS (SKIP TO SEC G IF EF> 35%)		Yes	No	Unreca
	26.3 Complex congential heart disease	Y	N	U

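### One-year hospitalizations come from a different source, and on a different time anchor, for SOLVD trial participants than for other Registry patients

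*Protocol*

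**What the plan says.** Protocol section IX (Follow-up Data) sets two routes to the one-year information.

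- **Patients outside the trials.** A follow-up form is mailed. Its question (i) asks about hospitalizations over a period that the clinic fills in as one year from enrollment. If mail fails, telephone and other means are used, and the form may be completed by telephone.
- **Trial participants.** "If the participant is participating in the SOLVD trials, DO NOT attempt a mail or phone contact by the Registry". Instead, "Contact information is to be obtained from the closest scheduled SOLVD trial visit occurring after one year from the SOLVD REGISTRY BASELINE FORM". Only the ladder of life is described as unavailable from the trial. For that item the protocol says "it must be administered at a visit close to the one year time", with the answer entered on the Registry Follow-up Form.

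For living patients, the nurse retrieves hospital reports when a hospitalization has occurred. If none is known, nothing further is required. For patients who have died, the nurse obtains hospitalization reports and the death documents.

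Section III says "It is anticipated that at least 20% of the Registry patients at each center will also be in the SOLVD trials". The trial section of the Registry Baseline Form (Section F) carries the instruction "SKIP TO SEC G IF EF> 35", and the Introduction names marked systolic dysfunction as the key trial entry criterion. The Registry itself admits patients with EF up to 45%, or with radiologically confirmed heart failure.

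Section II lists one-year morbid events, their relation to baseline covariates, and a comparison of follow-up events with the Trials as subsidiary objectives 2, 3 and 5. Section X models morbid events as it models death, with EF among the example covariates. No rule reconciles the two sources.

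**The concern.** The same endpoint is measured in two ways, and the way is fixed by a patient characteristic that is tied to EF. For a living non-trial patient, an admission that is not mentioned on the form has no other described way into the data. For a trial participant, the information passes through scheduled trial follow-up. If the two routes find different fractions of admissions, part of any observed difference between trial and non-trial patients is an artefact, and so is a smaller part of any difference across EF.

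The time anchors differ as well. Question (i) runs one year from enrollment, which section IX defines as the date of the earliest qualifying measurement. The trial visit is located by reference to the Baseline Form, which may reach the Coordinating Center up to 90 days after logbook registration.

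The subsidiary morbidity objectives are at stake, most directly the comparison with the Trials. The hospitalization question also cannot be put back after data collection has ended.

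**Working it through.** The plan gives no hospitalization rate, capture rate or morbidity power, so there is no stated figure to reproduce. Table 1 concerns mortality only. What follows is an illustration under assumed inputs.

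**Inputs from the protocol**

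- Registry size: "It is expected that around 6000 patients will be enrolled".
- Trial share: "at least 20% of the Registry patients at each center will also be in the SOLVD trials", hence 0.20 × 6,000 = 1,200 trial-route patients and 4,800 others.
- All trial-route patients are taken to have EF ≤ 35%, following the Baseline Form skip.
- Two-sided 0.05 level (section VI).

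**Assumptions (not in the documents)**

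- True one-year hospitalization risk h is the same in every group: 30% or 50%.
- Capture is t by the trial route and s by questionnaire recall.
- f is the share of EF ≤ 35% patients who are in the trials. If 40%, 50% or 60% of the Registry has EF ≤ 35%, then f = 0.20/0.40 = 0.50, 0.20/0.50 = 0.40 or 0.20/0.60 = 0.33.

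**Formulas**

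- Observed risk = h × capture.
- Spurious trial/non-trial ratio: r = t/s.
- Spurious EF ≤ 35% versus > 35% ratio: [f·t + (1 − f)·s]/s = 1 + f(r − 1).

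**Set A: t = 100%, f = 0.40**

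| s | r | EF ratio |
|---|---|---|
| 90% | 1.11 | (0.40 + 0.54)/0.90 = 1.04 |
| 80% | 1.25 | (0.40 + 0.48)/0.80 = 1.10 |
| 70% | 1.43 | (0.40 + 0.42)/0.70 = 1.17 |

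**Set B: t = 95%, f = 0.33 to 0.50**

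| s | r | EF ratio | Chance of a falsely significant trial excess, h = 30% | Same, h = 50% |
|---|---|---|---|---|
| 90% | 1.06 | 1.02-1.03 | 18% | 34% |
| 85% | 1.12 | 1.04-1.06 | 56% | 88% |
| 80% | 1.19 | 1.06-1.09 | 89% | about 100% |
| 70% | 1.36 | 1.12-1.18 | about 100% | about 100% |

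The last two columns use the normal approximation for two proportions, with pooled variance under the null and unpooled variance under the alternative. For h = 30% and s = 85%, the observed risks are 0.285 and 0.255 and the pooled risk is 0.261. The standard errors are 0.01417 (null) and 0.01447 (alternative). Then z = (0.030 − 1.96 × 0.01417)/0.01447 = 0.15, which gives 56%. With equal capture the chance is 2.5% in each direction. The same formula reproduces ten of the eleven one-year mortality powers in Table 1 to within 2 points. The exception, case 5, does not bear on this point.

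Across both sets r runs from 1.06 to 1.43 and the EF ratio from 1.02 to 1.18. Combining the extremes of both (t = 100%, s = 70%, f = 0.50) would give 1 + 0.50 × 0.43 = 1.21. If the trial route captured less than recall, every ratio would fall below 1.

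**Time anchor.** Suppose the Baseline Form is dated 90 days after enrollment and events are counted up to a visit one year after that. The trial window is then 365 + 90 = 455 days against 365, and 455/365 = 1.25, or about 25% longer. A visit that late would also fall outside the 60 days after the enrollment anniversary that section IX allows for submitting the one-year forms.

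**The case against.** Several stronger readings are tempting, and the documents do not support them.

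- **That non-trial patients are asked only once, by mail.** Telephone and other means follow if mail fails, and the nurse retrieves reports of known admissions. For deaths, the nurse obtains the reports directly. What remains is a single one-year recall for surviving non-trial patients.
- **That the questionnaire is forbidden for trial participants.** Only mail or telephone contact by the Registry is barred. The Follow-up Form is used for their ladder-of-life answer. How its question (i) is to be completed for them is not stated.
- **That trial visits find more admissions, so low EF will show false excess morbidity.** The text says "Contact information is to be obtained from the closest scheduled SOLVD trial visit occurring after one year". That hospitalizations come from the same source is a fair inference, because only the ladder of life is called unavailable. But this document gives neither the trial visit schedule nor how visits record admissions, so better trial capture is plausible and not shown.
- **That the trial window is definitely longer.** The visit anchor differs, but the protocol does not say that events up to the visit are counted.

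It can also be said that using trial contact avoids following the same patients twice, and that the EF bias is diluted because many low-EF patients are outside the trials. The EF bias can also be handled in analysis, since trial status is on the Baseline Form and the covariates in section X are only examples. An analysis plan that is not shown may already do so. All of this stands. It limits the size and reach of the point, but it does not supply a common question or window, which analysis cannot create afterwards.

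**Conclusion.** The point holds in limited form. The protocol fixes the source and time anchor of one-year hospitalizations by trial status, for at least 20% of patients, all at low EF, with no rule to reconcile the two. The effect is most direct on comparisons of trial with non-trial patients and on objective 5, and is diluted across EF.

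The trial/non-trial ratio of about 1.06-1.43 and the EF ratio of about 1.02-1.18 are illustrations. They rest on assumed capture of 70-90% by recall and 95-100% by the trial route, on equal true risks, and on an assumed share of low-EF patients in the trials. At a 5-point capture gap the EF effect is 2-3%. It becomes material at gaps of about 15 points or more.

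A reader might infer that the primary outcome is compromised. It is little affected, because long-term vital status is sought from death registries whatever the trial status.

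**What to change.** 1. At the trial visit near one year where the ladder of life must already be administered, also complete question (i) of the Registry Follow-up Form for trial participants. Use the enrollment-anchored one-year dates, as for everyone else. If that visit falls before the anniversary, cover the remaining days at the next one.
2. Record the source of each hospitalization (mail, telephone, visit or trial record).
3. Use question (i) as the common source for comparisons within the Registry, with trial records as a sensitivity analysis.
4. Report morbidity, and its relation to EF, by trial status, or within non-trial patients, or adjusted for trial status.

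If capture then became equal, the spurious ratios would return to 1.00 and the false-positive rate to the nominal 5% two-sided. In practice a difference between answering in person and by mail would remain. Comparing trial records with question (i) would therefore give only an indication, probably a lower bound, of what mailed recall misses. It would not remove the capture difference against the Trials' own event data in objective 5, which should be stated as a limitation there.

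The cost is about a minute of staff time per trial participant, plus a possibly less complete source for these patients in the common-source analysis. Step 4 needs no new data.
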